4.5 Selection and Timing of Dose for Each Subject

BMS-986205 will be administered orally daily at the doses listed in [Section 3.1.5](#)

Each subject will be assigned to a specific dose level as listed in [Section 4](#) in sequential order during dose escalation Part 1. Subjects in dose expansion Part 2 will be treated at the MTD, the MAD, or at an alternate dose determined from Part 1, if agreed upon by the investigators and the Sponsor. Subjects treated in Part 3 will receive BMS-986205 at 100 mg daily and will receive doses and schedules of nivolumab and ipilimumab selected for each tumor-specific expansion cohort as detailed in [Section 3.1.7](#).

In Parts 1 and 2, Nivolumab will be administered intravenously as flat doses; either 240 mg Q2W for the Part 1 dose escalation and for the Part 2 dose expansion cohorts that predated Amendment 06, or 480 mg Q4W for the Part 2 dose expansion cohorts added with or after Amendment 06 (melanoma, NSCLC, RCC, and additional signal-seeking tumors) and the clinical pharmacology substudy. In Part 3, nivolumab will also be administered in flat doses for all cohorts at the specified doses for those cohorts.

There will be no dose escalations or reductions of nivolumab allowed once assigned. Subjects receiving nivolumab Q2W will be dosed no less than 12 days from the previous dose and no more than 3 days from the scheduled dose. Subjects receiving nivolumab Q3W may be dosed 21 days (\pm 3 days) from the previous dose. Subjects receiving nivolumab Q4W may be dosed 28 days (\pm 3 days) from the previous dose.

For subjects receiving ipilimumab, the dosing calculations should be based on the body weight. If the subject's weight on the day of the dosing differs by $> 10\%$ from the weight used to calculate the dose, the dose must be recalculated. All doses should be rounded up or to the nearest milligram per institutional standard. There will be no dose modifications of ipilimumab allowed. Subjects receiving ipilimumab Q3W may be dosed no less than 19 days from the previous dose and no more than 3 days from the scheduled dose. Subjects receiving ipilimumab Q6W may be dosed every 42 days (\pm 3 days). Subjects receiving ipilimumab Q8W may be dosed every 56 days (\pm 3 days).

When nivolumab and ipilimumab are scheduled to be dosed on the same day, if dosing is delayed, both nivolumab and ipilimumab must be delayed together. If dosing is resumed after a dose delay, both nivolumab and ipilimumab must be resumed on the same day if the next scheduled day includes both nivolumab and ipilimumab administration.

There are no premedications recommended for nivolumab or ipilimumab (where applicable) on the first cycle. If an acute infusion reaction is noted, the subjects should be managed according to [Section 4.7.1](#).

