The starting dose of BMS-986205 is 25 mg orally daily. Nivolumab will be administered at a dose of 240 mg Q2W for the dose escalation (Part 1) and for the dose expansion (Part 2) cohorts that predated Amendment 06. Nivolumab will be administered at a dose 480 mg intravenously Q4W for the dose expansion cohorts added with and after Amendment 06 (melanoma, NSCLC, and additional signal-seeking tumors; renal cell carcinoma) and the clinical pharmacology substudy.

A schematic of Parts 1 and 2 and the pharmacologic substudy is provided in [Figure 1](#).

Figure 1: Study Design Schematic for Parts 1 and 2 and Clinical Pharmacology Substudy

*Note: As of Amendment 06, dose escalation beyond 400 mg BMS-986205 may not occur provided that additional pharmacodynamic effect is unlikely.

**Note: The BRAF mutated, post-BRAFi regimen melanoma subjects will be randomized to receive either nivolumab or BMS-986205 + nivolumab.

Abbreviations: CNS = central nervous system; CTLA-4 = cytotoxic T lymphocyte-associated antigen 4; DLBCL = diffuse large B-cell lymphoma; I-O = immuno-oncology; MAD = maximum administered dose; MTD = maximum tolerated dose; Nivo = nivolumab; NSCLC = non-small cell lung cancer; PD-L = programmed cell death; PD-L1 = programmed death receptor-ligand 1; PD-(L)1 = either PD-1 or PD-L1; SCCHN = squamous cell carcinoma of the head and neck.

Please refer to [Table 3.1.6-1](#) in the protocol body for a detailed description of the Part 2 dose expansion cohorts.

Part 3: Part 3 will include the initial safety evaluation and cohorts of the combination of BMS-986205, nivolumab, and ipilimumab in melanoma, NSCLC, and bladder cancer. Subjects with each tumor type will receive BMS 986205 in combination with a different regimen of nivolumab and ipilimumab based on safety and efficacy data observed in previous trials of nivolumab and ipilimumab in that tumor type (see [Section 1.1](#) of the protocol).

For the safety cohorts, the initial dose level of BMS-986205 for each cohort will be based on the available of safety, PK, and PD data for BMS-986205 in combination with nivolumab and any available data from the combination with nivolumab and ipilimumab. The starting dose will not exceed 100 mg in any cohort.

The regimens will consist of:

Melanoma (Ipi 1Q8): BMS 986205 in combination with nivolumab 480 mg Q4W and ipilimumab 1 mg/kg Q8W, all given continuously.

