Selection of Dose for Dose Expansion (Part 2), Combination with Nivolumab and Ipilimumab (Part 3)

Based on the preliminary clinical safety, pharmacokinetic, and pharmacodynamic data observed to date, cohort expansion in Part 2 was opened using both 100 and 200 mg doses in combination with nivolumab. This initial selection of two doses for cohort expansion in Part 2 allowed for the continued accrual of data at both doses to support a final dose decision. After review of safety, PK, and PD data, 100 mg was selected as the dose to be used for remaining subject enrollment in Part 2. See [Section 1.4.4.4](#), for the description of clinical safety and tolerability of 100 and 200 mg and [Section 1.4.4.1](#) for a discussion of the preliminary pharmacokinetic profile.

For Part 3 of this study, the maximum initial dose of BMS-986205 evaluated will be 100 mg daily. The selection of 100 mg was based on the aggregate safety and PK data in combination with nivolumab across doses of BMS-986205 found to be safe and tolerable, as well as to provide an additional safety margin since the safety profile of BMS-986205 at 200 mg is acceptable in combination with nivolumab. Lower doses may be evaluated based on emerging safety, PK, and PD data.

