3.1.1.2 Part 3 (Combination with Both Nivolumab and Ipilimumab)

Part 3 is the safety evaluation and cohort expansion of the combination of BMS-986205, nivolumab, and ipilimumab. Initial safety evaluations will be performed in subjects with melanoma, NSCLC, and bladder cancer. Subjects with each tumor type will receive

BMS-986205 in combination with a different regimen of nivolumab and ipilimumab based on safety and efficacy data observed in previous trials of nivolumab and ipilimumab in that tumor type (see [Section 1.1](#)). After this initial safety evaluation, dosing regimens will then be evaluated in expansion cohorts, which may include subjects with other types of malignancies.

Subjects in safety evaluation cohorts will receive BMS-986205 at a dose which was shown to be tolerable in combination with nivolumab (from Parts 1 and 2) and nivolumab plus ipilimumab (from Part 3), as applicable. The dose of BMS-986205 will not exceed 100 mg daily.

The regimens will consist of:

- **Melanoma (Ipi 1Q8 regimen):** BMS-986205 in combination with nivolumab 480 mg Q4W and ipilimumab 1 mg/kg Q8W, all given continuously.
- **NSCLC (Ipi 1Q6 regimen):** BMS-986205 in combination with nivolumab 360 mg Q3W and ipilimumab 1 mg/kg Q6W, all given continuously.
- **Bladder (Ipi 3Q3 regimen):** BMS-986205 given continuously, first in combination with nivolumab 80 mg and ipilimumab 3 mg/kg both given Q3W for 4 doses, followed by nivolumab 480 mg Q4W continuously

[figure not shown]
Evaluation of each regimen will begin with an assessment of safety and tolerability of the triplet combination therapy in a limited number of subjects, including a sentinel subject (see [Section 3.1.7](#)), in a safety evaluation cohort. The melanoma and NSCLC safety cohorts will begin safety enrollment simultaneously since the dose of ipilimumab is similar between the cohorts. Furthermore, for nivolumab dosing, the 480 mg Q4W and 360 mg Q3W are expected to achieve similar average exposure. The safety evaluation for the bladder regimen will begin enrolling subjects once either the melanoma or NSCLC regimen has been found to be safe and tolerable, as the bladder regimen uses a higher dose (3 mg/kg Q3W) of ipilimumab relative to the melanoma and NSCLC cohorts (1 mg/kg Q6W and Q8W of ipilimumab) during the DLT evaluation period.

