3.1.7 Part 3: BMS-986205, Nivolumab, and Ipilimumab Combination

Part 3 of the study will include a initial safety evaluation cohorts of 3 regimens of nivolumab and ipilimumab in combination with BMS-986205 in melanoma, NSCLC, and bladder cancer. Expansion cohorts for each regimen will then be conducted in the tumor type evaluated in the safety cohorts. The Ipi 1Q8W regimen will also be evaluated in a mixed cohort of other tumor types evaluated in Part 2. Each tumor type will receive BMS-986205 in combination with a specific nivolumab and ipilimumab regimen (see [Section 3.1.1.2](#)).

For the safety cohorts, the initial dose level of BMS-986205 for each cohort will be based on the available of safety, PK, and PD data for BMS-986205 in combination with nivolumab and any available from the combination with nivolumab and ipilimumab. The starting dose will not exceed 100 mg in any safety cohort. Lower dose levels of BMS-986205 (if required) to be evaluated in each safety cohort will be based on [Table 3.1.5-1](#). Intermediate or lower doses, or less frequent dosing of BMS-986205 may be tested if none of the planned doses/schedules are found to be tolerated. In addition, alternative lower doses and more intermittent schedules of nivolumab and/or ipilimumab may be evaluated if the specified regimen used in each tumor type safety cohort is not found to be tolerable with any of the doses of BMS-986205 outlined in Table 3.1.5-1. Safety will be evaluated independently for each tumor type/regimen combination and treatment regimen based on DLTs using a BLRM-copula model.

All safety cohorts will begin with an assessment of safety and tolerability of the triplet combination regimen in a limited number of subjects. As described in Section 3.1.1.2, the NSCLC/Ipi 1Q6 and melanoma/Ipi 1Q8 regimen cohorts will begin enrollment first, followed by the bladder/Ipi 3Q3 regimen cohort once safety and tolerability have been established in either NSCLC/ Ipi 1Q6 or melanoma/Ipi 1Q8. Initially, approximately 3 subjects will be treated at the selected dose combination of BMS-986205 with nivolumab and ipilimumab. The first subject in each safety cohort will be a sentinel subject who will be observed for 5 days after administration of the first combination dose to ensure safety and tolerability before other subjects can receive treatment within that cohort.

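### Section 4.5 fixes the Part 3 BMS-986205 dose at 100 mg daily; elsewhere 100 mg is only a ceiling and the dose is chosen per tumor type/regimen cohort

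*Combined protocol and SAP*

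**What the plan says.** Section 4.5 opens with a general line, "BMS-986205 will be administered orally daily at the doses listed in" Section 3.1.5. It then gives one specific rule for Part 3: "Subjects treated in Part 3 will receive BMS-986205 at 100 mg daily". The rest of that sentence refers the reader to Section 3.1.7, but for the nivolumab and ipilimumab doses and schedules.

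The other Part 3 text runs differently:

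- Synopsis, Part 3: "The starting dose will not exceed 100 mg in any cohort".
- Section 1.1.6.1: "the maximum initial dose of BMS-986205 evaluated will be 100 mg daily", followed by "Lower doses may be evaluated based on emerging safety, PK, and PD data".
- Section 3.1.1.2: "The dose of BMS-986205 will not exceed 100 mg daily".
- Section 3.1.7: "The starting dose will not exceed 100 mg in any safety cohort", and "Lower dose levels of BMS-986205 (if required) to be evaluated in each safety cohort will be based on" Table 3.1.5-1.
- Sections 3.1.7 and 8.1.3, on expansion: no dose in mg is named. Each regimen uses the BMS-986205 dose found tolerable with it, and under Section 3.1.7 the mixed tumor cohort takes the dose chosen for melanoma expansion.

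**The concern.** A reader who goes to the section titled for dose selection finds a single fixed dose. A reader who goes to the design sections finds a dose that depends on the cohort and may be lower. Both texts stand in Revised Protocol 05, so this is not a leftover in an amendment log.

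The fixed figure is also the highest dose allowed, so anyone following it literally would err upward. Section 1.5.3 says the BMS-986205 dose may be related to the hepatic toxicity seen with the triplet. There is a compliance side as well. Section 9.1.1 requires the study to be run as the protocol describes, yet a subject correctly assigned 50 mg or 25 mg is off the dose that Section 4.5 states.

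**Working it through.** The point involves no power, alpha or precision figure. The check sets the texts side by side and counts subjects by dose.

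**1. What each place does with 100 mg**

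| Place | Role of 100 mg | Lower doses |
|---|---|---|
| Section 4.5 | Fixed dose for Part 3 | Not mentioned in that sentence |
| Synopsis, Part 3 | Maximum starting dose | Provided for |
| Section 1.1.6.1 | Maximum initial dose | Provided for |
| Section 3.1.1.2 | Ceiling | Compatible |
| Section 3.1.7, safety cohorts | Maximum starting dose | Provided for, from Table 3.1.5-1 |
| Sections 3.1.7 and 8.1.3, expansion | Not named | Tolerable dose per regimen |

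Section 4.5 stands alone.

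**2. Doses in use at 3 May 2018 (Section 1.4.4.4, described there as preliminary)**

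- Melanoma: 2 DLTs in 4 evaluable subjects at 100 mg. The BLRM still allowed enrollment at that dose. The dose was lowered to 50 mg in view of the melanoma and NSCLC DLTs together. At 50 mg there were 0 DLTs in 3 evaluable subjects, and enrollment was continuing.
- NSCLC: 1 DLT in 1 evaluable subject at 100 mg, then 2 in 2 at 50 mg. Enrollment at 50 mg was then held per the BLRM analysis, and 25 mg was opened.
- Bladder: no dose reported.

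**3. Subjects by dose**

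- Melanoma: 4 at 100 mg + 4 at 50 mg = 8.
- NSCLC: 13 − 8 = 5 in total, of whom 3 were at 100 mg. That leaves 5 − 3 = 2, which matches the two evaluable subjects reported at 50 mg and leaves none yet treated at 25 mg.
- Totals: 4 + 3 = 7 at 100 mg and 4 + 2 = 6 at 50 mg; 6/13 = 46%.

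The NSCLC count at 50 mg comes from subtraction and is not stated. Section 1.5.3 gives 11 treated subjects instead of 13. With 11, 11 − 8 − 3 = 0 would remain for NSCLC at 50 mg, against the two evaluable subjects reported there, so 13 is used.

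**4. Whether anything in Section 4.5 rescues the sentence**

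- The reference to Section 3.1.7 attaches grammatically to nivolumab and ipilimumab, so it does not qualify the BMS-986205 dose.
- The opening line points to the dose list of Section 3.1.5. That list contains 25, 50 and 100 mg but does not say which one a Part 3 cohort is on.
- Section 4.5.3 covers reductions in individual subjects after adverse events. It does not set a cohort's assigned dose.

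**The case against.** The strongest reply is that this is one unaligned sentence with little practical reach. Under Section 4.4 the site calls the IVRS before first dosing to obtain the treatment assignment. Tables 5.1-4 and 5.1-5 repeat the IVRS assignment on Days 1 and 29 (melanoma and mixed) and Days 1 and 22 (NSCLC), the same days on which BMS-986205 is dispensed. Section 3.1.7 holds the detailed rules, and the 50 mg subjects show that practice followed them. This stands as mitigation. It does not make the sentence correct, and the IVRS and pharmacy manuals that Section 5.2 says are supplied separately cannot be examined here.

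A second reply is that the opening line's pointer to Section 3.1.5 is useful for Part 3, because Section 3.1.7 takes its lower dose levels from Table 3.1.5-1. That is right. A reader might infer that the pointer exposes Part 3 subjects to the table's higher levels, up to 800 mg. The 100 mg limits in Sections 3.1.1.2 and 3.1.7 rule that out, so the opening line is not part of the fault.

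A reader might also infer that 100 mg had been shown to be unsafe in melanoma. Section 1.4.4.4 does not support that, since the model still permitted it, and the DLT counts are too small to estimate a rate.

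**Conclusion.** The inconsistency is real and should be fixed: an operative dosing sentence in the current protocol is wrong as written. Its size is a stated dose of 100 mg against 50 mg enrolling in melanoma and 25 mg opened in NSCLC at the 3 May 2018 snapshot. Those gaps describe the text; they do not measure harm.

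A reader might infer that subjects were overdosed, or that the BLRM or ORR results are biased. The documents show neither. They also do not say whether subjects already on 100 mg were moved to a lower dose. Nor do they show how Section 4.5 read when the 50 mg subjects were treated, so those subjects cannot be called protocol deviations.

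One part rests on inference. Section 3.1.7 states no 100 mg cap for expansion, and the cap in Section 3.1.1.2 directly follows text on the safety cohorts. The cap carries over because safety cohorts start at 100 mg or less, only lower levels are named for them, and at least 6 DLT-evaluable subjects must be assessed at a dose before that regimen's expansion opens.

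**What to change.** Replace the Part 3 sentence in Section 4.5 with wording such as: *In Part 3, each subject takes BMS-986205 once daily at the dose assigned at enrollment for the tumor type/regimen cohort under Section 3.1.7, never above 100 mg, subject to the dose modifications in Section 4.5.3; nivolumab and ipilimumab follow Sections 3.1.1.2 and 3.1.7.*

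Anchoring the dose at enrollment matters. Wording tied to the cohort's current dose could be read as switching subjects already on 100 mg whenever the cohort dose drops. That would sit badly with Section 3.1.2, which continues subjects beyond 48 weeks on their originally assigned regimen, and with the individual reductions in Section 4.5.3. If the sponsor does want such subjects switched, the protocol should say so explicitly.

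Editing the opening line is optional. If it is changed, keep Table 3.1.5-1 as the source of the lower Part 3 dose levels.

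The cost is one sentence in the next amendment. An administrative letter would serve if the sponsor regards the change as a clarification of Section 3.1.7; under Section 9.1.1 investigators then inform their ethics committees. Sample size, safety monitoring and analysis are unaffected.

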4.5.1 Dose-limiting Toxicities

For the purpose of guiding dose escalation, DLTs will be defined based on the incidence and grade of AEs for which no alternate cause can be identified.

Part 1: Cycle 0 (BMS-986205 monotherapy lead-in) will have a 2-week DLT evaluation period (DLT 1). The combination regimen will have 4-week DLT evaluation period (DLT 2). Therefore, the total DLT assessment period is 6 weeks in Part 1. Subjects may proceed from Cycle 0 to Cycle 1 at each cohort unless any of the following events are observed: any DLT, Grade 2 or higher immune-related AEs considered related to BMS-986205 (eg, immune-mediated pneumonitis, colitis, hepatitis, nephritis, renal dysfunction) with the exception of immune-mediated hypothyroidism and hyperthyroidism, or Grade 2 AST or ALT elevation that does not resolve to Grade 1 within 1 week. For Grade 2 AST or ALT elevations that resolve to Grade 1 or baseline within 1 week, subjects can be rechallenged with BMS-986205 monotherapy for a minimum of 5 days before proceeding to combination with nivolumab provided there is not a recurrence of Grade 2 event.

The DLT-evaluation interval begins on the first day of treatment and continues for 6 weeks. The DLT 1 period is 14 days, and subjects must receive 75% of the BMS-986205 monotherapy doses to be considered evaluable for combination with nivolumab. The DLT 2 period is 4 weeks during which subjects will receive daily dosing of BMS-986205 and 2 doses of nivolumab. The total DLT period is 6 weeks, and subjects must have received at least 75% of BMS-986205 doses and 2 doses of nivolumab with observation for a minimum of 5 days following the second combination therapy dose to be considered evaluable for dose escalation decisions. Based on the predicted human half-life of BMS-986205 of 23 hours, this interval is expected to cover the anticipated time frame for the occurrence of clinically significant immediate and early onset AEs related to BMS-986205 monotherapy during Cycle 0 and repeat dosing of BMS-986205 in combination with nivolumab in Cycle 1.

Part 3: The DLT-assessment period is 6 weeks in Part 3 for all treatment regimens evaluated. The DLT-evaluation interval begins on the first day of treatment and continues for 6 weeks.

DLT-evaluable subjects will be defined as subjects who in the 6 week DLT evaluation period received $\geq 75\%$ of BMS-986205 doses and the following nivolumab and ipilimumab doses for each regimen:

- Melanoma/Ipi 1Q8: 2 doses of nivolumab and 1 dose of ipilimumab, and followed for at least 5 days after the second dose of nivolumab

- NSCLC/Ipi 1Q6: 2 doses of nivolumab and 1 dose of ipilimumab, and followed for at least 5 days after the second dose of nivolumab
- Bladder/Ipi 3Q3: 2 doses of nivolumab and 2 doses of ipilimumab, and followed for at least 5 days after the second dose of each drug

The incidence of DLTs that occur within 6 weeks following the start of study drug will guide dose escalation decisions. AEs will be graded according to the NCI CTCAE v4.03. For the purposes of subject management, drug-related AEs occurring at any time that meet the DLT definition will lead to dose interruption, dose modifications, and/or permanent discontinuation of study drug as defined in [Section 4.5.3](#) and [Section 4.5.6](#). Subjects who withdraw from the study during the DLT evaluation interval for reasons other than a DLT may be replaced at the same dose level. The incidence of DLT(s) during the DLT evaluation period will be used in dose escalation decisions and to define the MTD. AEs occurring after the DLT period will be considered for the purposes of defining the MTD, upon agreement between the Sponsor/Medical Monitor and investigators, if they are determined to have no clear alternative cause and are not related to disease progression.

AEs will be graded according to the NCI CTCAE v4. For the purpose of guiding dose escalation, DLTs are defined below based on the incidence and grade of AEs for which no alternative cause can be identified.

In addition to the criteria listed below, any drug-related toxicity that results in a subject not being able to receive at least 75% of the doses of BMS-986205 and all pre-specified doses (see above) of nivolumab and ipilimumab (where applicable) during the DLT evaluation period or causing greater than 2 weeks of dose delay may be classified as a DLT.

DLTs for DLT1 and DLT2 Periods in Part 1 and the entire DLT evaluation period in Part 3

Nonhematologic Dose-limiting Toxicity (DLT):

A. Hepatic Nonhematologic DLT

Any of the following events will be considered a hepatic DLT:

- Any \geq Grade 3 elevation of AST, ALT, or total bilirubin
- Grade 2 AST or ALT with symptomatic liver inflammation (eg, right upper quadrant tenderness, jaundice, pruritus)
- AST or ALT $> 3 \times$ ULN and concurrent total bilirubin $> 2 \times$ ULN without initial findings of cholestasis (elevated serum alkaline phosphatase, eg, findings consistent with Hy's law or FDA definition of potential drug-induced liver injury [DILI])*

*Note that this special category of DLT uses ULN rather than Common Toxicity Criteria Grade for definition.

B. Nonhepatic Nonhematologic DLT

Any of the following events will be considered a nonhepatic nonhematologic DLT:

- Grade 2 or greater episcleritis, uveitis, or iritis
- Any other Grade 2 eye pain or blurred vision that does not respond to topical therapy and does not improve to Grade 1 severity within 2 weeks OR requires systemic treatment
- Grade 2 myocarditis
- Grade 3 pneumonitis, bronchospasm, neurologic toxicity, hypersensitivity reaction, or infusion reaction of any duration requires discontinuation
- Any Grade 3 or greater nondermatologic, nonhepatic, nonhematologic toxicity will be considered a DLT with the following specific EXCEPTIONS:
 - Grade 3 or Grade 4 electrolyte abnormalities that are not complicated by associated clinical adverse experiences, last less than 48 hours and either resolve spontaneously or respond to conventional medical intervention
 - Grade 3 nausea, vomiting, or diarrhea that lasts less than 48 hours and either resolves spontaneously or responds to conventional medical intervention
 - Isolated Grade 3 elevation of amylase or lipase not associated with clinical or radiographic evidence of pancreatitis
 - Isolated Grade 3 fever not associated with hemodynamic compromise (eg, hypotension, clinical or laboratory evidence of impaired end-organ perfusion)
 - Grade 3 endocrinopathy that is well-controlled by hormone replacement
 - Grade 3 tumor flare (defined as pain, irritation, or rash that localizes to site of known or suspected tumor)
 - Grade 3 fatigue
 - Grade 3 infusion reaction that returns to Grade 1 in less than 6 hours

C. Dermatologic DLT

- Grade 3 rash if no improvement (ie, resolution to \leq Grade 1) after a 1- to 2-week infusion delay. Subjects who have not experienced a Grade 3 drug-related skin AE may resume treatment in the presence of Grade 2 skin toxicity.
- Grade 4 rash of any duration

D. Hematologic DLT

- Methemoglobin levels \geq 15%
- Grade 4 neutropenia \geq 5 days in duration
- Grade 4 thrombocytopenia or Grade 3 thrombocytopenia with bleeding, or any requirement for platelet transfusion
- Grade \geq 3 febrile neutropenia for 48 hours
- Grade \geq 3 hemolysis (ie, requiring transfusion or medical intervention such as steroids)
- Grade 4 anemia not explained by underlying disease

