4.5.6 Guidelines for Permanent Discontinuation

Subjects will be required to permanently discontinue all study drugs for the following AEs:

- Clinical deterioration, as assessed by the investigator
- Any occurrence of serotonin syndrome
- Any Grade 3 non-skin, drug-related AE lasting > 7 days, or recurs with the following exceptions for laboratory abnormalities, neurologic toxicity, drug-related uveitis, pneumonitis, bronchospasm, hypersensitivity reactions, infusion reactions, endocrinopathies (and diarrhea and colitis for subjects receiving ipilimumab):
 - Grade 3 drug-related neurologic toxicity, uveitis, pneumonitis, bronchospasm, myocarditis, hypersensitivity reaction, or infusion reaction of any duration requires discontinuation; for subjects receiving ipilimumab, Grade 3 diarrhea and colitis of any duration also require discontinuation
 - Grade 3 drug-related endocrinopathies, adequately controlled with only physiologic hormone replacement do not require discontinuation. Adrenal insufficiency requires discontinuation regardless of control with hormone replacement.
 - Grade 3 drug-related laboratory abnormalities do not require treatment discontinuation except:
 - ◆ Grade 3 drug-related thrombocytopenia > 7 days or associated with bleeding requires discontinuation
 - ◆ Any drug-related liver function test (LFT) abnormality that meets the following criteria require discontinuation:
 - Grade ≥ 3 drug-related AST, ALT or Total Bilirubin requires discontinuation*
 - Concurrent AST or ALT $> 3 \times$ ULN and total bilirubin $> 2 \times$ ULN

* In most cases of Grade 3 AST or ALT elevation, study treatment will be permanently discontinued. If the investigator determines a possible favorable benefit/risk ratio that warrants continuation of study treatment, a discussion between the investigator and the BMS Medical Monitor/designee must occur.

- Any Grade 4 drug-related adverse event or laboratory abnormality (including but not limited to creatinine, AST, ALT, or Total Bilirubin), except for the following events which do not require discontinuation:
 - Grade 4 neutropenia ≤ 7 days
 - Grade 4 lymphopenia or leukopenia or asymptomatic amylase or lipase

- Isolated Grade 4 electrolyte imbalances/abnormalities that are not associated with clinical sequelae and are corrected with supplementation/appropriate management within 72 hours of their onset

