administrations. If necessary, corticosteroids (up to 25 mg of SoluCortef or equivalent) may be used.

Late-occurring symptoms:

In the case of late-occurring hypersensitivity symptoms (eg, appearance of a localized or generalized pruritus within 1 week after treatment), symptomatic treatment may be given (eg, oral antihistamine or corticosteroids).

For Grade 3 or Grade 4 symptoms: Severe reaction; Grade 3: prolonged (eg, not rapidly responsive to symptomatic medication and/or brief interruption of infusion); recurrence of symptoms following initial improvement; hospitalization indicated for other clinical sequelae (eg, renal impairment, pulmonary infiltrates); Grade 4: life-threatening; pressor or ventilatory support indicated.

Immediately discontinue study drug infusion. Begin an IV infusion of normal saline and treat the subject as follows: recommend bronchodilators, epinephrine 0.2 to 1 mg of a 1:1,000 solution for subcutaneous administration or 0.1 to 0.25 mg of a 1:10,000 solution injected slowly for IV administration, and/or diphenhydramine 50 mg IV with methylprednisolone 100 mg IV (or equivalent), as needed. Subject should be monitored until the investigator is comfortable that the symptoms will not recur. Study drug will be permanently discontinued. Investigators should follow their institutional guidelines for the treatment of anaphylaxis. Remain at bedside and monitor subject until recovery from symptoms. In the case of late-occurring hypersensitivity symptoms (eg, appearance of a localized or generalized pruritus within 1 week after treatment), symptomatic treatment may be given (eg, oral antihistamine or corticosteroids).

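### Section 4.5.1 lists a brief Grade 3 infusion reaction both as a DLT and as an exception; its short-diarrhea exemption also sits unexplained beside the ipilimumab stopping rule

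*Combined protocol and SAP*

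**What the plan says.** Part B of the DLT list in Section 4.5.1 names events that count as nonhepatic, nonhematologic DLTs. One line is "Grade 3 pneumonitis, bronchospasm, neurologic toxicity, hypersensitivity reaction, or infusion reaction of any duration requires discontinuation". A later, general line makes other Grade 3 or worse toxicities DLTs, subject to named exceptions. Two of the exceptions are "Grade 3 infusion reaction that returns to Grade 1 in less than 6 hours" and "Grade 3 nausea, vomiting, or diarrhea that lasts less than 48 hours and either resolves spontaneously or responds to conventional medical intervention".

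The list is headed "DLTs for DLT1 and DLT2 Periods in Part 1 and the entire DLT evaluation period in Part 3", so one set of rules serves both parts. Just before it, a catch-all covers drug-related toxicity that keeps a subject from at least 75% of BMS-986205 doses and all required antibody doses in the window, or one "causing greater than 2 weeks of dose delay may be classified as a DLT".

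Section 4.5.6 lists reasons to stop all study drugs permanently. Among them: "Grade 3 drug-related neurologic toxicity, uveitis, pneumonitis, bronchospasm, myocarditis, hypersensitivity reaction, or infusion reaction of any duration requires discontinuation", and "for subjects receiving ipilimumab, Grade 3 diarrhea and colitis of any duration also require discontinuation". Section 4.7.1, on Grade 3 or 4 infusion reactions, says "Study drug will be permanently discontinued".

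**The concern.** A DLT list has to give the same answer to everyone who applies it. Here a Grade 3 infusion reaction that settles in four hours is a DLT on one line and exempt on another.

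The count goes to two places. It is the data for the BLRM-copula model that guides the BMS-986205 dose. It is also the numerator of the 33% rule in Section 3.1.7, which covers each tumor type and regimen in Part 3 and is applied to about the first six subjects of each tumor type in the mixed cohort before more are enrolled. Under Appendix 1, Sections 3.2.1 and 3.2.2, results from Part 1 also become priors for Part 3, so an inconsistent Part 1 count carries forward.

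The diarrhea exemption raises a lesser question. Every Part 3 regimen gives ipilimumab on Day 1. A brief episode of drug-related Grade 3 diarrhea therefore ends all study treatment there, yet the DLT list exempts it, and the protocol does not say whether that is intended.

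**Working it through.** The plan gives no figure to reproduce, so the check is a comparison of the texts plus some arithmetic on the windows and the trigger.

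**Infusion reaction, Grade 3, back to Grade 1 within 6 hours**
- Section 4.5.1, specific line: a DLT, whatever its duration.
- Section 4.5.1, exception: not a DLT.
- Sections 4.5.6 and 4.7.1: permanent stop.

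The exceptions hang on the general Grade 3 line, not on the specific one. By structure the specific line governs, the event is a DLT, and the exception has no effect. Reading the specific line as covering only reactions that require discontinuation changes nothing, because Section 4.5.6 requires it at any duration. No reading gives both lines work to do.

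The catch-all also reaches this event. Part 3 infusions in the window fall on Day 1 and on Day 22 (NSCLC, bladder) or Day 29 (melanoma, mixed). A permanent stop on those days leaves at most 22/42 = 52.4% or 29/42 = 69.0% of BMS-986205 doses, below 75%. But that clause says the event may be classified as a DLT, not that it will be.

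**Diarrhea, Grade 3, under 48 hours, Part 3**
- Section 4.5.1: exempt.
- Section 4.5.6: all study drugs stop.
- Catch-all, dose-shortfall limb: the window is 6 weeks, or 42 daily doses. 0.75 × 42 = 31.5, so 32 doses are needed (31/42 = 73.8%; 32/42 = 76.2%). With no missed dose this is met on Day 32, after the second nivolumab dose in every regimen. From Day 32 to Day 42 (11 of 42 days, 26.2%) the limb no longer applies. Each missed BMS-986205 dose moves the cut-off a day later.
- Catch-all, delay limb: the text does not say whether a permanent stop is a delay of more than two weeks.

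So for diarrhea on Day 36 lasting 36 hours, counting is possible only if the stop is treated as a delay and the optional clause is then used.

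**What one event can do to the 33% rule** (smallest k with k/n above the limit; denominator is all treated subjects)

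| n | limit 0.33 | limit one third |
|---|---|---|
| 6 | 2 (33.3%) | 3 (50.0%) |
| 12 | 4 (33.3%) | 5 (41.7%) |
| 40 | 14 (35.0%) | 14 (35.0%) |

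At n = 6, one event fewer is 1/6 = 16.7% or 2/6 = 33.3%, and the rule is not crossed. These figures show how sensitive the rule is to one event. They do not estimate how often such an event occurs.

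**Reported data** (Section 1.4.4.4): DLTs in 2/4 and 0/3 evaluable melanoma subjects (100 and 50 mg) and in 1/1 and 2/2 NSCLC subjects (100 and 50 mg). All are hepatic.

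**The case against.** The structure of the list already settles the infusion reaction, so the exception may be no more than a leftover line. DLT rules and stopping rules also serve different purposes: Section 4.5.1 defines DLTs to guide dose escalation and treats stopping as subject management. Diarrhea and colitis are known effects of nivolumab and ipilimumab (Section 1.1.6.3), so stopping cautiously while not letting a short, resolving episode drive the BMS-986205 dose is defensible. Other safeguards exist. Dose decisions draw on all available data (Appendix 1, Section 2.3), the sponsor reviews adverse events continuously (Section 1.5.1), and the melanoma dose was cut from 100 to 50 mg while the model still allowed enrollment. Crossing 33% leads to discussion and possible interruption, not an automatic stop.

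Most of this stands, and it keeps the point small. It does not remove the contradictory line, and it does not tell an assessor which count to enter. For diarrhea, the defensible choice is not stated to be a choice.

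A reader might go further and infer that toxicities ending treatment escape the Part 3 DLT count. The documents do not support that. The structural reading counts the infusion reaction, the catch-all permits counting either event before about Day 32, and no missed event is reported. A reader might also infer that every permanent discontinuation ought to be a DLT. Section 4.5.1 says DLTs lead to interruption, modification or discontinuation. It does not say the reverse.

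**Conclusion.** Minor. Section 4.5.1 contradicts itself on a Grade 3 infusion reaction that settles within 6 hours. The better reading makes it a DLT, but the text leaves room for two counts. The diarrhea exemption is a real mismatch with Section 4.5.6 for subjects on ipilimumab. It may be deliberate, and the dose-shortfall limb lapses only in Days 32 to 42, assuming no missed BMS-986205 dose.

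The effect on a model recommendation cannot be computed, because the documents give neither the frequency of these events nor the updated priors. Nothing in the documents shows that a dose decision was affected. Confidence is high on the wording and low on any practical effect.

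**What to change.** 1. Delete the under-6-hours infusion-reaction exception from Section 4.5.1. The list then agrees with Sections 4.5.6 and 4.7.1.
2. Limit the short-diarrhea exception to subjects not receiving ipilimumab, or state that the difference from Section 4.5.6 is intended. Limiting it leaves the Part 1 definition unchanged, since Part 1 gives no ipilimumab.
3. Check subjects already assessed for DLTs for affected events: for infusion reactions, Part 1 (its combination period, as the oral lead-in has no infusions) and Part 3; for diarrhea, Part 3 only, if the exception is limited. Section 1.4.4.4 reports 13 Part 3 subjects treated as of 3 May 2018; about 30 were planned for Part 1. The priors and the Part 3 data then rest on one definition.

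Do not add a general rule that any permanent discontinuation is a DLT. It would bring in events not on the list, such as Grade 3 thrombocytopenia beyond 7 days without bleeding, and would change the Part 1 definition more widely.

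The cost is two short edits and the check. The DLT count may rise slightly, including for antibody toxicity that may not reflect the BMS-986205 dose. Subject management does not change.
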